3. IDENTIFICATION OF POTENTIAL HY'S LAW CASES

In order to identify cases of PHL it is important to perform a comprehensive review of laboratory data for any patient who meets any of the following identification criteria in isolation or in combination:

- ALT ≥3xULN
- AST ≥3xULN
- TBL ≥2xULN

When a patient meets any of the identification criteria, in isolation or in combination, the central laboratory will immediately send an alert to the Investigator (also sent to Aegerion representative).

The Investigator will also remain vigilant for any local laboratory reports where the identification criteria are met, where this is the case the Investigator will:

- Notify the Aegerion representative
- Request a repeat of the test (new blood draw) by the central laboratory
- Complete the appropriate unscheduled laboratory CRF module(s) with the original local laboratory test result

When the identification criteria are met from central or local laboratory results the Investigator will without delay:

• Determine whether the patient meets PHL criteria (see Section 2 of this Appendix for definition) by reviewing laboratory reports from all previous visits (including both central and local laboratory results).

The Investigator will without delay review each new laboratory report and if the identification criteria are met will:

- Notify the Aegerion representative
- Determine whether the patient meets PHL criteria (see Section 2 of this Appendix for definition) by reviewing laboratory reports from all previous visits
- Promptly enter the laboratory data into the laboratory CRF

Confidential Page 5 of 11

4. FOLLOW-UP

4.1 Potential Hy's Law Criteria not met

If the patient does not meet PHL criteria the Investigator will:

- Inform the Aggerion representative that the patient has not met PHL criteria.
- Perform follow-up on subsequent laboratory results according to the guidance provided in the Clinical Study Protocol.

4.2 Potential Hy's Law Criteria met

If the patient does meet PHL criteria the Investigator will:

- Determine whether PHL criteria were met at any study visit prior to starting study treatment (See Section 6)
- Notify the Aegerion representative who will then inform the central Study Team

The Study Physician contacts the Investigator, to provide guidance, discuss and agree an approach for the study patients' follow-up and the continuous review of data. Subsequent to this contact the Investigator will:

- Monitor the patient until liver biochemistry parameters and appropriate clinical symptoms and signs return to normal or baseline levels, or as long as medically indicated.
- Investigate the etiology of the event and perform diagnostic investigations as discussed with the Study Physician. This includes deciding which tests available in the Hy's law lab kit should be used.
- Complete the three Liver CRF Modules as information becomes available.
- If at any time (in consultation with the Study Physician) the PHL case meets serious criteria, report it as an SAE using standard reporting procedures.

Confidential Page 6 of 11

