8. SAFETY REPORTING AND MEDICAL MANAGEMENT

The Principal Investigator is responsible for ensuring that all staff involved in the study is familiar with the content of this section.

All adverse events, including SAEs, adverse events leading to discontinuation, and AESIs will be recorded on the eCRF. Additionally, all SAE and AESI that require immediate reporting will be captured on the SAE/AESI form and sent to the pharmacovigilance department (see Section 8.6).

Confidential Page 36 of 58

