8.2 Definitions of Serious Adverse Events

An SAE is an AE occurring during any study phase (i.e., run-in, treatment, wash-out, follow-up), that fulfills one or more of the following criteria:

- Results in death
- Is immediately life-threatening
- Requires in-patient hospitalization or prolongation of existing hospitalization
- Results in persistent or significant disability/incapacity or substantial disruption of the ability to conduct normal life functions
- Is a congenital abnormality or birth defect
- Is an important medical event that may jeopardize the patient or may require medical intervention to prevent one of the outcomes listed above

For further guidance on the definition of an SAE, refer to Appendix A.

In addition, for the purposes of this protocol, the following adverse events of special interest (AESI) must be handled as SAEs and are reportable to Aegerion or designee (see Section 8.6) within the SAE timeframe regardless whether the adverse events did not meet the serious criteria described above in this section:

- The presence of Category D or E *in vitro* neutralizing activity (or the relevant corresponding test result from the ligand-binding method) to metreleptin
- Necrotizing pancreatitis
- Hepatic adverse events including potential DILI

Confidential Page 37 of 58

- Severe hypoglycaemia
- Severe hypersensitivity reactions
- New diagnoses of autoimmune disorders (for instance, autoimmune hepatitis, glomerulonephritis, lupus erythematosus, antiphospholipid antibody syndrome, rheumatoid arthritis)
- Autoimmune disease exacerbation
- Serious infection resulting in hospitalization
- All cancers (excluding non-melanoma skin cancer) by cancer type
- Exposed pregnancies and pregnancy outcomes

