8.3.6 Adverse Events Based on Examinations and Tests

The results from protocol-mandated laboratory tests and vital signs will be summarized in the clinical study report. Deterioration, as compared to baseline, in protocol-mandated laboratory values and vital signs should be reported as.

8.3.7 Any new or aggravated clinically significant abnormal medical finding at a physical examination as compared with the baseline assessment should also be reported. Hy's Law

Cases where a patient has an AST or ALT $\ge 3x$ ULN and total bilirubin $\ge 2x$ ULN may need to be reported as SAEs. Refer to Appendix B for further instruction in cases of combined increase of aminotransferase and total bilirubin.

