8.4 Reporting of Serious Adverse Events

All SAEs must be reported, whether or not considered causally related to the investigational product, or to the study procedure(s). All SAEs will be recorded in the eCRF.

Should an SAE occurs during the course of the study, Investigators or other site personnel must inform Aegerion or designee per Section 8.6 within 1 day, i.e., immediately but **no later than 24 hours** of when he or she becomes aware of it.

The designated Aegerion representative or designee will work with the Investigator to ensure that all the necessary information is provided to the Aegerion Patient Safety data entry site **in a timely manner** for fatal and life-threatening events of initial receipt for all other SAEs

For all SAEs, including fatal or life-threatening, where important or relevant information is missing, active follow-up is undertaken immediately. Investigators or other site personnel inform Aegerion representatives or designee of any follow-up information on a previously reported SAE within 1 calendar day, i.e., immediately but **no later than 24 hours** of when he or she becomes aware of it.

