1. INTRODUCTION

This Appendix describes the process to be followed in order to identify and appropriately report cases of Hy's Law. It is not intended to be a comprehensive guide to the management of elevated liver biochemistries. During the course of the study the Investigator will remain vigilant for increases in liver biochemistry. The Investigator is responsible for determining whether a patient meets potential Hy's Law (PHL) criteria at any point during the study.

The Investigator participates, together with Aegerion clinical project representatives, in review and assessment of cases meeting PHL criteria to agree whether Hy's Law (HL) criteria are met. HL criteria are met if there is no alternative explanation for the elevations in liver biochemistry other than Drug Induced Liver Injury (DILI) caused by the Investigational Medicinal Product (IMP).

The Investigator is responsible for recording data pertaining to PHL/HL cases and for reporting Adverse Events (AE) and Serious Adverse Events (SAE) according to the outcome of the review and assessment in line with standard safety reporting processes.

Confidential Page 3 of 11

2. **DEFINITIONS**

Potential Hy's Law (PHL)

Aspartate Aminotransferase (AST) or Alanine Aminotransferase (ALT) $\ge 3x$ Upper Limit of Normal (ULN) together with Total Bilirubin (TBL) $\ge 2x$ ULN at any point during the study following the start of study medication irrespective of an increase in Alkaline Phosphatase (ALP).

Hy's Law (HL)

AST or ALT $\ge 3x$ ULN **together with** TBL $\ge 2x$ ULN, where no other reason, other than the IMP, can be found to explain the combination of increases, e.g., elevated ALP indicating cholestasis, viral hepatitis, another drug.

For PHL and HL the elevation in transaminases must precede or be coincident with (i.e., on the same day) the elevation in TBL, but there is no specified timeframe within which the elevations in transaminases and TBL must occur.

Confidential Page 4 of 11

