5. REVIEW AND ASSESSMENT OF POTENTIAL HY'S LAW CASES

The instructions in this Section should be followed for all cases where PHL criteria are met.

No later than 3 weeks after the biochemistry abnormality was initially detected, the Study Physician contacts the Investigator in order to review available data and agree on whether there is an alternative explanation for meeting PHL criteria other than DILI caused by the IMP. The Aegerion Medical Science Director and Global Safety Physician will also be involved in this review together with other subject matter experts as appropriate.

According to the outcome of the review and assessment, the Investigator will follow the instructions below.

If there is an agreed alternative explanation for the ALT or AST and TBL elevations, a determination of whether the alternative explanation is an AE will be made and subsequently whether the AE meets the criteria for a SAE:

- If the alternative explanation is not an AE, record the alternative explanation on the appropriate CRF
- If the alternative explanation is an AE/SAE, record the AE/SAE in the CRF accordingly and follow the Aegerion standard processes

If it is agreed that there is no explanation that would explain the ALT or AST and TBL elevations other than the IMP:

- Report an SAE (report term 'Hy's Law') according to Aegerion standard processes.
 - The 'Medically Important' serious criterion should be used if no other serious criteria apply
 - As there is no alternative explanation for the HL case, a causality assessment of 'related' should be assigned.

If, there is an unavoidable delay, of over 3 weeks, in obtaining the information necessary to assess whether or not the case meets the criteria for HL, then it is assumed that there is no alternative explanation until such time as an informed decision can be made:

• Report an SAE (report term 'Potential Hy's Law') applying serious criteria and causality assessment as per above

Confidential Page 7 of 11

Appendix B: Actions Required in Cases of Increases in Liver Biochemistry and Evaluation of Hy's Law

• Continue follow-up and review according to agreed plan. Once the necessary supplementary information is obtained, repeat the review and assessment to determine whether HL criteria are met. Update the SAE report according to the outcome of the review

Confidential Page 8 of 11

6. ACTIONS REQUIRED WHEN POTENTIAL HY'S LAW CRITERIA ARE MET BEFORE AND AFTER STARTING STUDY TREATMENT

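### Section 8.2 makes potential drug-induced liver injury reportable within 24 hours whether or not it is serious, but Section 8.3.7 and Appendix B make the SAE report of a potential Hy's Law case conditional

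*Protocol*

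**What the plan says.** **General rule.** Protocol Section 8.2 lists AESIs that must be handled as SAEs. They are reportable "within the SAE timeframe regardless whether the adverse events did not meet the serious criteria described above in this section". The list includes "Hepatic adverse events including potential DILI". Section 8.4 gives the timeframe: for an SAE, site staff "must inform Aegerion or designee per Section 8.6 within 1 day". Section 8.6, to which 8.2 refers, sets the same 24 hours from awareness and names the SAE/AESI form. The opening of Section 8 says that SAEs and AESIs needing immediate reporting "will be captured on the SAE/AESI form and sent to the pharmacovigilance department".

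**Liver-specific rule.** Section 8.3.7 (Hy's Law) covers AST or ALT at least 3x ULN with total bilirubin at least 2x ULN. It says such cases "may need to be reported as SAEs. Refer to Appendix B for further instruction".

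Appendix B then gives these instructions:
- Section 1 makes the investigator responsible for "reporting Adverse Events (AE) and Serious Adverse Events (SAE) according to the outcome of the review and assessment".
- Section 4.2 calls for an SAE report if at any time "the PHL case meets serious criteria, report it as an SAE using standard reporting procedures".
- Section 5 sets the timing of the joint review: "No later than 3 weeks after the biochemistry abnormality was initially detected, the Study Physician contacts the Investigator". It requires an SAE report if the review finds no explanation other than the drug, or if the necessary information is delayed by more than 3 weeks. If the agreed explanation is not an adverse event, it asks only for a CRF entry.
- Section 7 calls for no action on a repeat episode without significant change when the earlier cause was the disease under study, with liver disease among its examples.

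Neither 8.3.7 nor Appendix B mentions the AESI rule in 8.2 or the 24-hour limit.

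**The concern.** The two sets of instructions meet in one patient: someone who crosses both liver thresholds on treatment, has no serious criterion met, and has not yet been reviewed. Section 8.2 makes the report mandatory and prompt. Section 8.3.7 and Appendix B make it depend on seriousness or on the result of a later review. No text says which governs.

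An investigator with an abnormal liver panel will most likely turn to the section written for that situation. Someone who follows it faithfully can leave a non-serious case off the SAE/AESI form until the review, or never file one. What is at stake is the completeness and timing of pharmacovigilance reporting for an event the sponsor itself chose to expedite.

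**Working it through.** No arithmetic applies. The check is to follow one patient through both sets of instructions.

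**Step 1. Does 8.2 cover the case?** Section 8.2 does not define potential DILI, and no text states that a PHL case is one. Appendix B Section 1 says Hy's Law is met when DILI caused by the drug is the only explanation left. Until the review has looked for other causes, a PHL case is therefore naturally potential DILI. This is an assumption, but it follows from the appendix's own definition.

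**Step 2. What does each rule require?**

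| Situation (no serious criterion met at detection) | 8.2 with 8.4 and 8.6 | 8.3.7 and Appendix B |
|---|---|---|
| PHL criteria just met | SAE/AESI form within 24 hours of awareness | Notify the sponsor's representative and start the work-up; SAE report only if the case becomes serious |
| Review finds no cause other than the drug | Already reported | SAE report at this point |
| Information delayed beyond 3 weeks | Already reported | SAE report at this point, under a potential Hy's Law term |
| Agreed cause is a non-serious hepatic adverse event | Reportable as an AESI in its own right | AE recorded in the CRF; SAE only if SAE criteria are met |
| Agreed cause is not an adverse event | First report already made | CRF entry only |

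The fourth row does not need the assumption in Step 1. Section 8.2 covers hepatic adverse events generally, yet Appendix B Section 5 still asks whether the event meets SAE criteria.

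**Step 3. Could Appendix B merely classify cases already reported under 8.2?** Its Section 5 argues against this. When information is late, it tells the investigator to report an SAE. Only after that does it speak of updating an SAE report. Had every case been handled as an SAE within 24 hours, the late instruction would be to update. The appendix is written as if no earlier report exists.

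**Step 4. What still reaches the sponsor?** Under Appendix B Section 3, the central laboratory alert goes at once to the investigator and the sponsor's representative. Section 4.2 adds notice to the representative and three liver CRF modules. None of these is the SAE/AESI form, and none carries the 24-hour limit.

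**The case against.** The strongest reply is that the rules are compatible. A site can file within 24 hours under 8.2 and use Appendix B for the formal Hy's Law assessment. The appendix never says to withhold an AESI report, and its references to standard reporting processes could take in 8.2 and 8.6. It is true that a site can satisfy both rules. But the liver text does not tell it to, the seriousness condition in Section 4.2 comes before the mention of standard procedures, and Step 3 shows that Section 5 presumes no earlier report.

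A second reply is that PHL is a laboratory threshold, while Section 8.1 counts only clinically significant abnormal results as adverse events. This is why the link between PHL and potential DILI is an assumption here. It weakens the point without removing it: a combined rise at these thresholds is the signal the appendix exists to catch.

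Three stronger readings are tempting, and the documents do not support them:

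- **A reader might infer that Appendix B replaces a 24-hour deadline with a 3-week one.** The 3 weeks is the latest date for the Study Physician to contact the investigator for the review. It is not a filing deadline, and the two periods should not be compared as if they were the same kind of clock.
- **A reader might infer that the AESI tables in SAP 17.1 depend on which rule a site followed.** The protocol sends all adverse events and AESIs to the eCRF, and the SAP does not say that AESIs are drawn from the expedited form. The count could move only if a case was never recorded as an adverse event.
- **A reader might infer that Section 7 cancels reporting of repeat episodes.** That section is framed around follow-up, review and assessment, so its no-action outcome can be read as no new work-up. It is unclear on reporting, but it does not waive it.

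**Conclusion.** The plan is wrong as written on a narrow point. Section 8.2 states a mandatory 24-hour report with no seriousness condition. The section and appendix written for the same laboratory picture state a conditional report and omit the 8.2 rule. A site following the liver-specific text can therefore miss the SAE/AESI form for a non-serious case.

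Severity is minor. The sponsor's representative hears of the case, and the two outcomes of most concern, confirmed Hy's Law and an assessment delayed beyond 3 weeks, must still be reported as SAEs. The immunogenicity analyses do not use these reports. The documents give no frequency of PHL cases, so the number of reports at risk cannot be estimated; if no patient meets the thresholds it is zero. For most situations the conclusion rests on treating an unreviewed PHL case as potential DILI.

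**What to change.** Let 8.2 govern the first report and let the appendix update it.

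1. **Section 8.3.7.** Replace the conditional wording with a requirement: every such case is reported as an AESI on the SAE/AESI form within 24 hours of awareness under 8.2, whether or not a serious criterion is met.
2. **Appendix B Section 4.2.** Add the same 24-hour report to the investigator's steps once PHL criteria are met.
3. **Appendix B Sections 1 and 5.** State that the review updates the report already filed.
4. **Appendix B Section 7.** State that no action means no new work-up and does not waive reporting under 8.2.

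Section 6 applies only to patients with liver metastases and needs no edit for this purpose. Nor does SAP 17.1 need a rule counting every PHL case as a hepatic AESI: where another cause has been agreed, that is a matter of preference.

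Optionally, list every patient who crosses the AST or ALT and bilirubin thresholds beside that patient's AESI records. The SAP change record dated 26 February 2025 already describes changes made after database lock, so this listing is the step that can still show whether any case was missed.

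The cost is a few sentences in the protocol and its appendix, plus one optional listing from chemistry already collected. No visits or samples are added.

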5. REVIEW AND ASSESSMENT OF POTENTIAL HY'S LAW CASES

The instructions in this Section should be followed for all cases where PHL criteria are met.

No later than 3 weeks after the biochemistry abnormality was initially detected, the Study Physician contacts the Investigator in order to review available data and agree on whether there is an alternative explanation for meeting PHL criteria other than DILI caused by the IMP. The Aegerion Medical Science Director and Global Safety Physician will also be involved in this review together with other subject matter experts as appropriate.

According to the outcome of the review and assessment, the Investigator will follow the instructions below.

If there is an agreed alternative explanation for the ALT or AST and TBL elevations, a determination of whether the alternative explanation is an AE will be made and subsequently whether the AE meets the criteria for a SAE:

- If the alternative explanation is not an AE, record the alternative explanation on the appropriate CRF
- If the alternative explanation is an AE/SAE, record the AE/SAE in the CRF accordingly and follow the Aegerion standard processes

If it is agreed that there is no explanation that would explain the ALT or AST and TBL elevations other than the IMP:

- Report an SAE (report term 'Hy's Law') according to Aegerion standard processes.
 - The 'Medically Important' serious criterion should be used if no other serious criteria apply
 - As there is no alternative explanation for the HL case, a causality assessment of 'related' should be assigned.

If, there is an unavoidable delay, of over 3 weeks, in obtaining the information necessary to assess whether or not the case meets the criteria for HL, then it is assumed that there is no alternative explanation until such time as an informed decision can be made:

• Report an SAE (report term 'Potential Hy's Law') applying serious criteria and causality assessment as per above

Confidential Page 7 of 11

Appendix B: Actions Required in Cases of Increases in Liver Biochemistry and Evaluation of Hy's Law

• Continue follow-up and review according to agreed plan. Once the necessary supplementary information is obtained, repeat the review and assessment to determine whether HL criteria are met. Update the SAE report according to the outcome of the review

Confidential Page 8 of 11

6. ACTIONS REQUIRED WHEN POTENTIAL HY'S LAW CRITERIA ARE MET BEFORE AND AFTER STARTING STUDY TREATMENT

This section is applicable to patients with liver metastases who meet PHL criteria on study treatment having previously met PHL criteria at a study visit prior to starting study treatment.

At the first on-study treatment occurrence of PHL criteria being met the Investigator will:

- Determine if there has been a significant change in the patients' condition[#] compared with the last visit where PHL criteria were met[#]
 - If there is no significant change no action is required
 - If there is a significant change notify the Aegerion representative, who will inform the central Study Team, then follow the subsequent process described is Section 4.2 of this Appendix

[#] A 'significant' change in the patient's condition refers to a clinically relevant change in any of the individual liver biochemistry parameters (ALT, AST or total bilirubin) in isolation or in combination, or a clinically relevant change in associated symptoms. The determination of whether there has been a significant change will be at the discretion of the Investigator, this may be in consultation with the Study Physician if there is any uncertainty.

Confidential Page 9 of 11

